## 7.2 Screening

A Screening Visit will take place up to 45 days prior to the Enrollment Visit (Day 0). Multiple visits may be conducted to complete all required screening procedures, if necessary. Written informed consent for Screening/Enrollment will be obtained before any screening procedures are initiated. For participants who do not meet the eligibility criteria, Screening will be discontinued once ineligibility is determined.

*Note: If a participant is ineligible based upon a behavioral criterion, the behavioral eligibility assessment may be completed in its entirety, to avoid socially desirable reporting.*

**Table 4: Visit 1- Screening Visit**

Visit 1-Screening Visit		
Component	Procedures	
Administrative and Regulatory	
 
• Obtain written informed consent
 
• Assess consent form comprehension
 
• Assign a unique Participant Identification (PTID) number
 
• Assess eligibility
 
• Collect demographic information
 
• Collect locator information
 
• Provide reimbursement
 
• Schedule next visit/contact*
 
	
Behavioral/Counseling	
 
• HIV pre- and post-test counseling
 
• HIV/STI risk reduction counseling
 
• Protocol counseling
 
	
Clinical	
 
• Collect medical history
 
• Collect concomitant medications
 
• Perform physical examination
 
• Perform rectal examination
 
• Disclose available test results
 
• Treat or prescribe treatment for RTI/UTI, or STIs*
 
	
Laboratory	Pharyngeal	
 
• Nucleic acid amplification test (NAAT) for GC/CT
 

	Urine	
 
• NAAT for GC/CT/Trichomonas
 
• Urine dipstick/culture*
 
• Pregnancy test φ
 

	Blood	
 
• HIV-1/2 test
 
• Syphilis serology
 

	Pelvic	
 
• NAAT for GC/CT and Trichomonasα
 

	Anorectal	
 
• NAAT for GC/CT
 
• HSV 1/2 detection* (at sites with capacity)
 

Study Product/Supplies	
 
• Offer condoms
 
• Offer lubricant **
 
	

\* If indicated and/or per local standard of care, \*\* Lubricant will be provided at product administration visits and as per local standard of care at other visits, φ Individuals who can get pregnant, α Individuals with a vagina or neovagina

### 7.3 Enrollment (Day 0)

The Enrollment Visit occurs up to 45 days after the Screening Visit. Participants will be randomized to study product application sequence and begin using study product at the clinic during this visit.

**Table 5: Visit 2- Enrollment Visit**

Visit 2- Enrollment Visit		
Component	Procedures	
Administrative and Regulatory	
 
Review informed consent/ confirm participant's willingness to participate in study
 
Assess and confirm eligibility
 
Review/update locator information
 
Provide reimbursement
 
Schedule next visit/contact*
 
Randomization
 
	
Behavioral/Counseling	
 
HIV pre- and post-test counseling
 
HIV/STI risk reduction counseling
 
Protocol counseling
 
Training in short message service (SMS)/instant message (IM) Reporting System
 
Baseline behavioral assessment
 
	
Clinical	
 
Review/update medical history
 
Review/update concomitant medications
 
Perform targeted physical examination
 
Perform rectal examination
 
Disclose available test results
 
Treat or prescribe treatment for RTI/UTI, or STIs*
 
	
Laboratory	Pharyngeal	
 
NAAT for GC/CT*
 

	Urine	
 
NAAT for GC/CT/Trichomonas*
 
Urine dipstick/culture*
 
Pregnancy test <math>\phi</math>
 

	Blood	
 
HIV-1/2 test
 
Plasma for archive
 
Syphilis serology*
 

	Pelvic	
 
NAAT for GC/CT/Trichomonas*□
 

	Anorectal	
 
NAAT for GC/CT*
 
HSV 1/2 detection* (at sites with capacity)
 

Study Product/Supplies	
 
Provide study product and study product use counseling
 
First study product application at the clinic
 
Offer condoms
 
Offer lubricant**
 
	

\* If indicated and/or per local standard of care, \*\* Lubricant will be provided at product administration visits and as per local standard of care at other visits, φ Individuals who can get pregnant, ♀ Individuals with a vagina or neovagina

## 7.4 Follow-up Visits

### 7.4.1 Visits 3, 5 and 7 – First, Second and Third Product Use End Visits (PUEV)

Visit 3 – First PUEV should occur 4 weeks (approximately 28 days) after the Enrollment Visit. Visit 5 – Second PUEV should occur 4 weeks (approximately 28 days) after Visit 4 – Product Switch Visit. Visit 7 – Third PUEV should occur 4 weeks (approximately 28 days) after Visit 6 – Product Switch Visit. The PSRT must be consulted regarding progression into the next dosing period prior to the initiation of study product for Periods 2 and 3, for any participant who has unresolved pelvic, genital or anorectal AEs of Grade ≥3, and any other AE that in the opinion of the investigator would preclude the participant from continuing to the next product use period.

Participants will complete brief, weekly short SMS/IM assessments about their product use and RAI behaviors during each 4-week product use period. Behavioral evaluations will be completed at the end of each product use period at Visits 3, 5, and 7, including a brief in-depth interview (IDI) during the visit to review their SMS/IM reports.

**Table 6: Visits 3, 5 and 7 – First, Second and Third PUEV**

Visits 3, 5 and 7 – First, Second and Third PUEV		
Component	Procedures	
Administrative and Regulatory	
 
Review/update locator information
 
Provide reimbursement
 
Schedule next visit/contact
 
	
Behavioral/Counseling	
 
HIV pre- and post-test counseling* (Required at Visit 7)
 
HIV/STI risk reduction counseling* (Required at Visit 7)
 
Protocol counseling
 
Behavioral assessment
 
Brief in-depth interview (IDI)
 
	
Clinical	
 
Review/update medical history
 
Review/update concomitant medications
 
Perform targeted physical examination*
 
Perform rectal examination
 
Disclose available test results
 
Record/update AEs
 
Treat or prescribe treatment for RTI/UTI, or STIs*
 
	
Laboratory	Pharyngeal	
 
NAAT for GC/CT* (Required at Visit 7)
 

	Urine	
 
Urine dipstick/culture*
 
NAAT for GC/CT/Trichomonas* (Required at Visit 7)
 
Pregnancy test* φ
 

Visits 3, 5 and 7 – First, Second and Third PUEV		
Component	Procedures	
	Blood	
 
HIV-1/2 test* (Required at Visit 7)
 
Syphilis serology* (Required at Visit 7)
 

	Pelvic	
 
NAAT for GC/CT/Trichomonas*ϣ (Required at Visit 7)
 

	Anorectal	
 
NAAT for GC/CT* (Required at Visit 7)
 
HSV 1/2 detection* (at sites with capacity)
 

Study Product/Supplies		
 
Offer condoms
 
Offer lubricant**
 

\* If indicated and/or per local standard of care, \*\* Lubricant will be provided at product administration visits and as per local standard of care at other visits, ϕ Individuals who can get pregnant, ϣ Individuals with a vagina or neovagina

#### 7.4.2 Visits 4 and 6 – Product Switch Visits

The Visit 4 – Product Switch Visit should occur 1 week (approximately 7 days) after Visit 3 – First PUEV. The Visit 6 – Product Switch Visit should occur 1 week (approximately 7 days) after Visit 5 – Second PUEV.

**Table 7: Visits 4 and 6 – Product Switch Visits**

Visits 4 and 6 – Product Switch Visits		
Component	Procedures	
Administrative and Regulatory	
 
Review/update locator information
 
Provide reimbursement
 
Schedule next visit/contact
 
	
Behavioral/Counseling	
 
HIV pre- and post-test counseling*
 
HIV/STI risk reduction counseling*
 
Protocol counseling
 
	
Clinical	
 
Review/update medical history
 
Review/update concomitant medications
 
Perform targeted physical examination*
 
Perform rectal examination*
 
Disclose available test results
 
Record/update AEs
 
Treat or prescribe treatment for RTI/UTI, or STIs*
 
	
Laboratory	Pharyngeal	
 
NAAT for GC/CT*
 

	Urine	
 
Urine dipstick/culture*
 
NAAT for GC/CT/Trichomonas*
 
Pregnancy test* ϕ
 

	Blood	
 
HIV-1/2 test*
 
Syphilis serology*
 

	Pelvic	
 
NAAT for GC/CT/Trichomonas*ϣ
 

	Anorectal	
 
NAAT for GC/CT*
 
HSV 1/2 detection* (at sites with capacity)
 

Visits 4 and 6 – Product Switch Visits	
Component	Procedures
Study Product/Supplies	
 
• Provide study product and study product use counseling
 
• Study product application at the clinic
 
• Offer condoms
 
• Offer lubricant**
 

\* If indicated and/or per local standard of care, \*\* Lubricant will be provided at product administration visits and as per local standard of care at other visits, φ Individuals who can get pregnant, Ϙ Individuals with a vagina or neovagina

### 7.4.3 Visit 8 – Final/Early Termination Visit

The Visit 8 – Final Visit should occur 1 week (approximately 7 days) after Visit 7 – Third PUEV. This visit will serve as the participant’s study termination.

During their Final or Early Termination Visit, participants will complete a conjoint analysis assessment to compare among the study products. Also, a subset of participants (approximately 10 per site) will be selected to complete an IDI during this visit to further explore participants’ acceptability of the study products.

**Table 8: Visit 8 – Final/Early Termination Visit**

Visit 8 – Final/Early Termination Visit		
Component	Procedures	
Administrative and Regulatory	
 
• Review/update locator information
 
• Provide reimbursement
 
	
Behavioral/Counseling	
 
• HIV pre- and post-test counseling*
 
• HIV/STI risk reduction counseling*
 
• Behavioral assessment
 
• IDI (subset)
 
	
Clinical	
 
• Review/update medical history
 
• Review/update concomitant medications
 
• Perform targeted physical examination*
 
• Perform rectal examination*
 
• Disclose available test results
 
• Record/update AEs
 
• Treat or prescribe treatment for RTI/UTI, or STIs*
 
	
Laboratory	Pharyngeal	
 
• NAAT for GC/CT*
 

	Urine	
 
• Urine dipstick/culture*
 
• NAAT for GC/CT/Trichomonas*
 
• Pregnancy test φ
 

	Blood	
 
• HIV-1/2 test*
 
• Syphilis serology*
 

	Pelvic	
 
• NAAT for GC/CT/Trichomonas*Ϙ
 

	Anorectal	
 
• NAAT for GC/CT*
 
• HSV 1/2 detection* (at sites with capacity)
 

Visit 8 – Final/Early Termination Visit	
Component	Procedures
Study Product/Supplies	
 
• Offer condoms
 
• Offer lubricant**
 

\* If indicated and/or per local standard of care, \*\* Lubricant will be provided at product administration visits and as per local standard of care at other visits, φ Individuals who can get pregnant, ☐ Individuals with vagina or neovagina

## 7.5 Follow-up Procedures for Participants Who Permanently Discontinue Study Product

### 7.5.1 Participants Who Become Infected with HIV-1/2

If a participant tests positive for HIV-1/2 after the Enrollment Visit, s/he will be referred to local care and treatment services and may return to the research clinic for additional counseling and other support services, as needed. Continued study participation would be of no added benefit; thus follow-up visits will be discontinued and the participant will be considered terminated from the study. An Early Termination Visit will be conducted, if the participant is willing. Participants who are taking oral PrEP for HIV prevention while on study and seroconvert after randomization may be offered additional laboratory testing (such as HIV RNA and HIV drug resistance testing), as clinically indicated, per discussions between the site IoR and LC. Please reference the MTN-035 SSP Manual for additional details ([www.mtnstopshiv.org/research/studies](http://www.mtnstopshiv.org/research/studies)).

### 7.5.2 Participants Who Become Pregnant

Any participant who becomes pregnant will be referred to local health care services and may return to the research clinic for additional counseling, as needed. Continued study participation would be of no added benefit to the participant, thus follow-up visits and procedures will be discontinued and the participant will be considered terminated from the study. An Early Termination Visit will be conducted, if the participant is willing. See [Section 9.7](#) for additional details.

### 7.5.3 Participants Who Permanently Discontinue Study Product for Other Reasons

For participants who permanently discontinue use of one of the study products for any clinician-initiated reason, the PSRT should be consulted regarding continued study participation and progression to other study products. For participants terminated from the study after PSRT consult, an Early Termination Visit will be conducted, if the participant is willing. See [Section 9](#) for additional details regarding clinical follow-up of AEs unresolved at the time of study termination.

Participants who permanently discontinue use of one of the study products for any self-initiated reason during the first or second product use period will be allowed to continue in the study and progress to the other study product(s), if they are willing. Participants who permanently discontinue study product use for any self-initiated reason during the

third product use period will be terminated from the study, and an Early Termination Visit will be conducted, if the participant is willing. See [Section 9.8](#) for additional details.

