## **7.8 Behavioral Evaluations**

All participants will respond to computer assisted self-interviews (CASI) at the Enrollment Visit (Visit 2) and at the three PUEVs (Visits 3, 5 and 7), and to a conjoint analysis assessment at the Final Visit (Visit 8). The assessment done at enrollment will include, among other topics, questions on participants' prior experiences and comfort using rectal products, as well as douching or other rectal hygiene practices. The follow-up

assessments will explore reactions to each study product and administration method, including participants' perceptions of their partners' reactions. These assessments will allow investigators to identify product attributes likely to challenge and/or facilitate future sustained use when applied rectally by participants. Suggestions for product improvement will also be collected. The conjoint analysis assessment will compare between the three study products, including questions on participant preferences regarding the different formulations.

Participants will also complete a brief weekly report of product use via SMS/IM for each study product. A brief IDI is planned for all participants at the three PUEVs (Visits 3, 5 and 7). These IDIs will review and explore participants' responses to acceptability, tolerability, and adherence questions asked via SMS/IM during each product use period.

Based on Behavioral Research Working Group (BRWG) review of SMS/IM data, approximately 10 participants per site will be selected and invited to complete a longer IDI at the Final Visit (Visit 8). This IDI will include questions comparing user acceptability of the study products, user-centered suggestions for product design and delivery, acceptability and factors influencing product use, douching history and education, and experiences with the application methods, among other topics. Suggestions for product improvement will also be collected. The audio from the IDI will be recorded and transcribed for analysis. The interview notes, recording and transcript will be considered as source documentation.

Major components of both CASI and IDI assessments have been used successfully and validated in prior rectal microbicide trials (e.g., MTN-006, MTN-007, MTN-017) and are being implemented/planned as part of MTN-026, MTN-033 and MTN-037.

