3. GENERAL DATA ANALYSIS CONSIDERATIONS

3.1 Analysis Set(s)

Safety endpoints will be assessed on a modified intent-to-treat analysis set, which will include all participants enrolled in the study who received at least one of the study products during the study. Primary acceptability, tolerability and adherence endpoints will be assessed on a per-protocol (PP) analysis subset, which will consist of participants who received all three study products and completed the corresponding product use end visits (PUEVs).

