8. PRIMARY ENDPOINTS

The acceptability, tolerability and adherence primary endpoints will be evaluated on the per-protocol subset of participants, i.e. participants who received all three study products and completed the corresponding PUEV, and thus provide relevant data from all three periods of study. Assessment of these endpoints will be based on responses from the participants to the computer assisted self-interviews (CASI) at the three PUEVs (Visits 3, 5 and 7). To aid in the interpretation of the resulting analyses, baseline characteristics of the per-protocol subset of participants including, but not limited to, study site, sequence, sex/gender, and age will be described and compared to those of participants who were lost to follow-up.

Acceptability and Tolerability

The acceptability and tolerability endpoint will be based on question H1 of the CASI:

“Think about the positive and negative experiences you have had using the rectal Insert during the past 4 week period. If this rectal insert was available and it provided some protection against HIV, how likely would you be to use it before receptive anal sex?”.

Responses to this question for each product were captured from visual Likert scale from 1 (very unlikely) to 10 (very likely). Participants’ responses corresponding to the three product use periods will be displayed in tables by study product, by study product and site and by study product and randomization sequence.

To compare acceptability and tolerability between study products, the endpoint will be operationalized as binary, with scores 1 to 6 grouped as “low acceptability” and scores 7 – 10 as “high acceptability”. Number and percentage of participants giving a “high acceptability” score will be display in tables by study product, with exact binomial 95% confidence intervals (Clopper-Pearson method).

Adherence

Two endpoints related to adherence will be assessed: adherence to use per-protocol and adherence to use per-anal-sex-act. These are defined as follows:

1. **Adherence to use per-protocol:** Number and proportion of participants who reported not having missed a rectal [enema/douche, insert or suppository] application in the previous 4 weeks, according to the participants’ response to question B0 of the CASI:

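### Participants who choose to stop their third product are terminated before Visit 7, and as written the Early Termination Visit does not include the product CASI that supplies the primary acceptability and adherence endpoints.

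*Protocol*

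**What the plan says.** Protocol 7.5.3 treats voluntary stopping differently by period. Participants who stop a product by choice "during the first or second product use period will be allowed to continue in the study", if they are willing. Those who stop during the "third product use period will be terminated from the study, and an Early Termination Visit will be conducted, if the participant is willing".

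Protocol 7.8 schedules "computer assisted self-interviews (CASI) at the Enrollment Visit (Visit 2) and at the three PUEVs (Visits 3, 5 and 7"). For the last visit, Protocol 7.4.3 says: "During their Final or Early Termination Visit, participants will complete a conjoint analysis assessment to compare among the study products". Table 8 and Appendix I show only a generic behavioural assessment at that visit, plus an in-depth interview in a subset.

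SAP 8 ties the primary acceptability and adherence endpoints to that instrument: "Assessment of these endpoints will be based on responses from the participants to the computer assisted self-interviews (CASI) at the three PUEVs". The items are H1 (likelihood of use, 1 to 10), B0 (weeks with a missed application), and B1 and B2 (sex acts, and acts preceded by product). SAP 3.1 restricts the primary analysis of these endpoints to "participants who received all three study products and completed the corresponding product use end visits (PUEVs"). Protocol 10.7.1 has the same restriction and adds a secondary analysis in all participants.

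Under SAP 3.2, multiple imputation applies only if more than 10% of data are missing, and it assumes ignorable missingness.

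**The concern.** Stopping a product voluntarily is itself information on adherence, and often on acceptability. In periods 1 and 2 a willing quitter stays in follow-up and can still answer the CASI for the abandoned product at its PUEV. In period 3 the quitter is terminated before Visit 7. Even if they attend the Early Termination Visit, the text does not have them asked H1 or B0 to B2 about the product they have just given up.

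There are two consequences. The product 3 answers are missing for a reason linked to the endpoint. And because the primary set requires all three PUEVs, the answers the same person already gave on products 1 and 2 leave the primary analysis as well.

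At stake are the per-product primary rates and, to a greater degree, anything read from period 3 alone. That includes the order-of-use assessment in Protocol 10.7.1 and SAP 10.

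**Working it through.** **1. The chain of rules**

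| Step | Period 1 or 2 quitter (willing to stay) | Period 3 quitter |
|---|---|---|
| Status (Protocol 7.5.3) | Continues | Terminated; Early Termination Visit if willing |
| Next behavioural instrument (Protocol 7.4.3, 7.8) | CASI at that period's PUEV | Conjoint task |
| H1, B0 to B2 for the stopped product | Can be obtained | Not scheduled |
| Primary set (SAP 3.1, 8) | Kept if all three products received and PUEVs done | Excluded for all three products |

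**2. The plan's own precision.** Protocol Table 9 (SAP Table 2) uses 200 evaluable participants. The exact two-sided 95% interval for 160/200 = 80% is (73.8, 85.3), which matches the stated (74, 85). The half-width is (85.3 − 73.8)/2, or about 6 points.

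**3. Direction.** SAP 8 defines full adherence as 0 weeks missed. Someone who stops for good part-way through a period will normally miss later weeks, so removing them raises that rate almost by definition. For acceptability, upward bias is likely but not certain, because the protocol allows any self-initiated reason.

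**4. Pooled per-product bias, quitting spread evenly.** The documents give no number of quitters, so these inputs are assumptions: true high-acceptability rate 70% for every product; a share q of the 210 quit in period 3; all quitters would rate the stopped product low; their ratings of the other two products are high at the 70% rate. Each product is third in two of the six sequences, so one third of quitters stop any given product.

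Rate in the primary set = 0.70 × (1 − 2q/3)/(1 − q)

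- q = 5%: 0.70 × 0.9667/0.95 = 71.2%, a bias of 1.2 points
- q = 10%: 0.70 × 0.9333/0.90 = 72.6%, a bias of 2.6 points, with 21 of 210 participants leaving the primary set

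**5. Quitting clustered on one product.** Suppose 10 quitters (about the whole planned 5% loss) all stop the same product, and the 200 completers show 160 high ratings.

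- Quitters excluded: 160/200 = 80.0%, 95% CI (73.8, 85.3)
- Quitters counted as low: 160/210 = 76.2%, 95% CI (69.8, 81.8)

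The difference is 3.8 points, and 70%, one of the Table 9 benchmarks, is no longer excluded.

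**6. Period 3 alone.** Each product has 2 × 35 = 70 participants in third position. Under the assumptions of step 4, the observed period-3 rate is 0.70/(1 − q): 73.7% at q = 5% and 77.8% at q = 10%, a shift of about 4 to 8 points. The right yardstick is the precision at n = 70: 49/70 = 70% has exact 95% CI (57.9, 80.4), a half-width of about 11 points.

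**The case against.** Several stronger readings are tempting, and the documents do not support them.

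- A reader might infer that nobody who disliked product 3 is ever rated. In fact anyone who dislikes it but attends Visit 7 answers the full CASI. The gap concerns only those who leave before that visit.
- A reader might treat upward bias in acceptability as established. Self-initiated reasons need not be dislike, the number of quitters is unknown, and losing their product 1 and 2 ratings could move those rates either way.
- A reader might conclude that the loss is beyond any analysis. SAP 6.1.3 tabulates early product stops with reasons, overall, by site and by sequence, so counting quitters as low is a feasible bound. The SAP does not plan it.
- A reader might compare the 4 to 8 point period-3 shift with the 6 point half-width at n = 200. That sets a subgroup figure against whole-sample precision.

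Other points reduce the expected size. The planned loss is 5% from all causes, so q = 5% already assigns all of it to period-3 quitters who would rate low. Some period 1 and 2 quitters will also decline to continue, which narrows the asymmetry. Order testing in the SAP is exploratory and done only if feasible.

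The procedures manual, to which Protocol 7 refers for detail, was not available and might add a CASI at early termination. Protocol 7.5.4 allows interim visits for missed procedures. Weekly message reports and the conjoint task also give some information from quitters.

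What stands: neither document assigns the product CASI to the Early Termination Visit, and SAP 8 does not use the message or conjoint data for the primary endpoints. The all-participant secondary analysis cannot supply answers that were not requested. Imputation below the 10% trigger is not planned, and above it the ignorability assumption fails where people leave because of the product.

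**Conclusion.** The gap is real and worth closing because it is cheap to close, but its expected effect on the primary estimates is small. Under the stated worst-case rating assumption and even spread, it inflates each pooled product rate by about 1.2 points at 5% period-3 quitting and 2.6 points at 10%. It matters more if quitting concentrates on one product: 10 such quitters take 80% to 76.2% and the lower limit from 73.8% to 69.8%. Period-3 rates, and therefore the exploratory order comparison, shift more, but with about 70 participants per product they are imprecise in any case.

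The direction is very likely upward for full adherence and probably upward for acceptability. All sizes rest on assumed quitter numbers and on every quitter rating the stopped product low. The conclusion concerns what the protocol and SAP specify; it could change if the procedures manual already requires the CASI at early termination.

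**What to change.** 1. **Protocol 7.4.3, 7.8, Table 8 and Appendix I.** When an Early Termination Visit takes place and the PUEV for a started product has not been done, give that product's PUEV CASI (at least H1, B0, B1 and B2) before the conjoint task.
2. **SAP 3.1 and 8.** Accept that CASI as the assessment for that product, so that participants who received all three products stay in the primary set. Flag answers based on less than 4 weeks of use and report a sensitivity analysis without them.
3. **SAP 3.2.** Regardless of the 10% trigger, add a sensitivity analysis that counts quitters with no CASI as low acceptability and non-adherent for the product they stopped. Report the number of period-3 quitters by product. This step is still possible if data collection has ended.

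The cost is a few minutes of an existing questionnaire at a visit already held, plus short additions to both documents. There are two downsides. Exposure lengths become mixed, although the items ask about the past 4 weeks. And quitters who decline the visit still give no data, which is why step 3 is needed. The termination rule itself is left as it is.
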